2.1 Study Design

This study was designed as a randomized controlled experimental trial with three parallel groups.

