2.5 Outcome Measures

Assessments were conducted at baseline and after the 8-week intervention period.

Primary outcome measures included:

- Cognitive functions assessed using standardized neuropsychological tests (e.g., Stroop Test, Visual-Auditory Digit Span Test)

Secondary outcome measures included:

- Motor performance assessments (Blaze Pod Reaction Time Test)
- Behavioral symptoms evaluated using parent-reported questionnaires (Conners Parent Rating Scale)

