2.6 Procedure

Baseline assessments were conducted prior to randomization. Following baseline measurements, participants were randomly assigned to one of the three groups. Exercise

interventions were conducted over an 8-week period. Post-intervention assessments were performed using the same measurement tools as at baseline.

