2.8 Statistical Analysis

A per-protocol analysis approach was used, and pre-test and post-test measurements were analyzed for all three groups. Statistical analyses were performed using SPSS software (IBM Corporation, Version 22, Armonk, NY, USA). One-way analysis of variance (ANOVA) and Pearson's chi-square test were used to analyze baseline demographic characteristics of the participants. To examine the primary outcome variables, a two-factor repeated measures analysis of variance (group \times time) with Bonferroni post hoc correction was applied. Within-group changes were analyzed using paired-samples t-tests. A p-value of less than 0.05 was considered statistically significant.

4. Results

Primary Outcomes

Cognitive Function

Cognitive function was assessed using the Stroop Test and the Visual-Auditory Digit Span Test. Changes from baseline to post-intervention scores were used to evaluate attention, executive functions, working memory, and cognitive processing speed. Both intervention groups demonstrated improvements in cognitive functions. The Gince Zumba group demonstrated greater gains in attention-related abilities, while the Square Stepping Exercise group showed more pronounced improvements in high-level cognitive functions."

Secondary Outcomes

Motor Performance

Motor performance was evaluated using the BlazePod Reaction Time Test. Changes in reaction time from baseline to post-intervention were analyzed. While both intervention groups exhibited significant improvements in motor performance relative to the control group, the enhancements were more pronounced in the Square Stepping Exercise group

Behavioral Symptoms

Behavioral outcomes were assessed using the Conners Parent Rating Scale. Changes in total and subscale scores from baseline to post-intervention were used to evaluate ADHD-related behavioral symptoms. Both intervention groups demonstrated significant reductions in ADHD-related behavioral symptoms relative to the control group and baseline measurements.

4. References

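### The primary group × time ANOVA with two time points is a change-score test: valid, but less precise than ANCOVA on the baseline score already collected before randomisation

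*Protocol*

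**What the plan says.** Protocol section 2.8 fixes the model for the primary cognitive outcomes: "To examine the primary outcome variables, a two-factor repeated measures analysis of variance", group by time, "with Bonferroni post hoc correction was applied". No covariate is named. The rest of the design bears on that choice:

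- Section 2.1: "This study was designed as a randomized controlled experimental trial with three parallel groups".
- Section 2.5: "Assessments were conducted at baseline and after the 8-week intervention period". There are two time points and no others.
- Section 2.6: "Baseline assessments were conducted prior to randomization", and "Post-intervention assessments were performed using the same measurement tools as at baseline".
- Results section, Cognitive Function: "Changes from baseline to post-intervention scores were used to evaluate attention" and other cognitive domains. The outcome is thus read on the change scale. The same paragraph reports findings ("Both intervention groups demonstrated improvements in cognitive functions"), so the results were known when this text was written.

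**The concern.** With two measurements per child, the group × time interaction asks whether mean change differs between arms. A change score subtracts the whole baseline value, as if the slope of post-test on baseline were 1. When the slope is below 1, part of the baseline noise is carried into the outcome. ANCOVA estimates the slope from the data instead. Because baseline precedes randomisation, both methods target the same between-group difference, so the choice between them is one of precision.

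The group contrasts on the primary outcomes are what is at stake, including the Results section's contrast between the two exercise programmes (attention against higher-level functions). The stated analysis gives these contrasts wider intervals and less power than the same data allow, although the covariate is already in hand.

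A related looseness is that section 2.8 does not say which contrast the Bonferroni comparisons test. If they are applied to the group factor, they compare means averaged over pre-test and post-test, which halves the treatment effect.

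**Working it through.** **Inputs from the protocol.** Three randomised arms (2.1); two assessments with the same tools (2.5, 2.6); baseline before randomisation (2.6); significance level 0.05 and Bonferroni correction (2.8).

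**Assumptions.** The protocol states no n, SD, effect size or pre-post correlation ρ, so there is no figure of its own to reproduce. I use ρ from 0.3 to 0.9, equal pre and post SDs set to 1, a true difference of 0.6 SD, 20 or 30 children per arm, and three two-sided pairwise comparisons at 0.05/3 = 0.0167.

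**Step 1: the interaction is a change-score test.** On one simulated data set (three arms of 15, two times), the group × time F was 3.4023 and the one-way ANOVA F on change was 3.4023.

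**Step 2: variances.**

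- Change score: v = 2(1−ρ)
- ANCOVA: v = 1−ρ²
- Ratio: (1−ρ²) / [2(1−ρ)] = (1+ρ)/2

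At ρ = 0.5 these are 1.00 and 0.75, a ratio of 0.75.

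**Step 3: power and interval width.** The standard error of a pairwise difference is √(2v/n). Power uses the noncentral t distribution with error df pooled over three arms: 3n−3 for change, 3n−4 for ANCOVA. The half-width is that of the 98.3% interval, in SD units. At n = 20 and ρ = 0.5:

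- Change: 2.467 × √(2 × 1.00/20) = 0.78
- ANCOVA: 2.468 × √(2 × 0.75/20) = 0.68

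Each cell after the ratio gives change, then ANCOVA.

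| ρ | Variance ratio | Power, n = 20 | Power, n = 30 | Half-width, n = 20 | n per arm for 80% power |
|---|---|---|---|---|---|
| 0.3 | 0.65 | 20%, 32% | 32%, 50% | 0.92, 0.74 | 83, 54 |
| 0.5 | 0.75 | 29%, 40% | 46%, 60% | 0.78, 0.68 | 60, 45 |
| 0.7 | 0.85 | 50%, 58% | 71%, 79% | 0.60, 0.56 | 36, 31 |
| 0.8 | 0.90 | 70%, 75% | 89%, 92% | 0.49, 0.47 | 25, 22 |
| 0.9 | 0.95 | 96%, 97% | 99.7%, 99.8% | 0.35, 0.34 | 13, 13 |

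**Step 4: simulation check.** With 40,000 simulated trials at n = 20, power for ρ = 0.3, 0.5, 0.7, 0.8, 0.9 was 20.0, 29.3, 50.0, 70.5, 95.9% for change and 31.5, 38.9, 56.9, 74.7, 96.6% for ANCOVA. The ANCOVA figures fall up to about 1 point below the formula because of chance baseline imbalance. Type I error was 1.6–1.8% (change) and 1.5–1.8% (ANCOVA) against a nominal 1.67%. Both tests hold their level.

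**Step 5: unequal SDs.** With k = SD post / SD pre, the ratio is k²(1−ρ²) / (1+k²−2ρk). For k of 0.8 to 1.2 and ρ of 0.5 to 0.8 it runs from 0.57 to 0.997. The gain nearly vanishes when the slope ρk is close to 1 (0.96 at k = 1.2, ρ = 0.8), but the ratio does not exceed 1.

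**Step 6: comparisons on the group factor.** Averaging pre and post gives an effect of 0.6/2 = 0.3 SD with variance (1+ρ)/2. At n = 20 the power is 11% at ρ = 0.3 and 7% at ρ = 0.9, against 20% and 96% for the change contrast.

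**The case against.** The strongest reply is that nothing in the protocol is wrong here. A group × time ANOVA suits two assessments, holds its type I error and agrees with the Results section's talk of changes. The size of the loss is unknown: at ρ = 0.9 and n = 20 the assumed power gain is about 1 point, and at ρ = 0.8 the half-width falls only from 0.49 to 0.47 SD. The results already exist, so sample-size figures cannot help this trial. A second analysis added now also raises the question of which one governs if the two disagree. Section 2.5 lists the primary tests only as examples, so the number of added models is open. An unseen SAP might already hold an adjusted analysis.

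Much of this is fair. The point concerns efficiency, and the sample-size column serves only to show scale. The reassurance about validity also has a limit: it applies to the randomised groups, whereas section 2.8 adopts a per-protocol approach, which can bias the comparison under either model. That is a separate issue.

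The objection does not remove the point. Section 2.8 itself fixes the primary model, so this is not a detail merely left to an SAP. The direction of the loss does not depend on the unknown figures; only its size does. The adjustment needs no new data. The risk of post hoc switching is met by keeping the stated ANOVA in the report and declaring the addition.

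**Conclusion.** The concern holds as a matter of precision and should be addressed. The stated primary test is a change-score test. Under randomisation it is unbiased with correct type I error, but it makes less efficient use of the baseline than ANCOVA. With equal SDs, ANCOVA's variance is 5% lower at ρ = 0.9 and 35% lower at ρ = 0.3. The loss is material at low to moderate correlation and small at 0.8 or higher. The ratio depends on ρ and the SDs; the power, interval and sample-size figures rest also on the assumed 0.6 SD effect, arm sizes and three Bonferroni comparisons. None of these inputs is in the protocol, so the loss in this trial cannot be stated.

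**What to change.** Add to section 2.8:

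> Each primary outcome's post-test score is analysed by ANCOVA with group as factor and the same outcome's baseline score as covariate. The three baseline-adjusted pairwise group differences are reported with Bonferroni-adjusted p-values and confidence intervals. This analysis was added after the results were known and is reported beside the originally stated group × time ANOVA.

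Where the ANOVA is kept, add:

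> Bonferroni comparisons are between-group differences in change from baseline to post-test, not group means averaged over the two assessments.

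The cost is one further model per primary outcome in the same SPSS version, and one degree of freedom for the covariate, which is negligible except in very small arms. No new data are needed. Because results are already described, the ANCOVA must be declared as a post-results addition and must not silently replace the stated ANOVA.

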2.3 Randomization and Groups

Participants were randomly assigned to one of three groups:

- 1. Gince Zumba Group (GZG)**
- 2. Square Stepping Exercise Group (SSEG)**
- 3. Control Group**

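### Bonferroni on the three pairwise comparisons is valid but needlessly conservative; a stepwise procedure such as Holm keeps the same 5% familywise error with more power

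*Protocol*

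**What the plan says.** Section 2.1 describes a "randomized controlled experimental trial with three parallel groups": Gince Zumba, Square Stepping and control (section 2.3). Section 2.5 gives two time points: "Assessments were conducted at baseline and after the 8-week intervention period". Section 2.8 examines the primary outcome variables with "a two-factor repeated measures analysis of variance" (group × time) and adds that this "with Bonferroni post hoc correction was applied". The threshold is given as "A p-value of less than 0.05 was considered statistically significant", without sidedness.

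Section 2.8 does not say which pairs the correction covers, whether it applies to the interaction or to group means, or whether the comparisons depend on a significant interaction. The results that follow interpret each exercise arm against control, for example "both intervention groups exhibited significant improvements in motor performance relative to the control group", and also compare the two exercise arms with each other. That fits all three pairs being tested, but it is an inference. The document states no sample size, effect size, SD or power.

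**The concern.** Bonferroni divides 0.05 by three for every pair, whatever the other pairs show. With exactly three groups the three null hypotheses are logically tied: if any two pairs are equal, so is the third. Once one pair has been shown to differ, at most one of the remaining nulls can be true, and testing at 0.0167 from there on is stricter than 5% familywise control requires.

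The loss falls on the comparisons the trial interprets: each exercise programme against control, and one programme against the other. The arm-against-arm difference is likely to be the smallest of the three, and the loss is greatest for the smaller differences.

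**Working it through.** **Inputs from the Protocol.** Three arms, so 3 pairs; two time points, so the interaction F test is the one-way F test on change scores; alpha 0.05 (two-sided assumed). There is no sample size or power figure to reproduce.

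**Assumed inputs.** 20 per arm, with 15 and 30 as a range; pre/post correlation 0.7; normal scores with SD 1 at each visit. The SD of change is then √(2 × (1 − 0.7)) = 0.775, so a shift of 0.6 SD is 0.6/0.775 = 0.77 SD of change.

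**Procedures compared.**
- Bonferroni: each p against 0.05/3 = 0.0167.
- Holm: ordered p-values against 0.05/3, 0.05/2 and 0.05, stopping at the first failure.
- Shaffer (three groups): smallest p against 0.05/3; if rejected, the other two in order against 0.05.
- Closed test: interaction F at 0.05; if significant, each pair at 0.05.

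**Error control.** For exactly three arms, any two pairwise nulls together are the global null, so Shaffer and the closed test both hold the familywise error at 5%. Holm does so for any number of comparisons. In simulation with equal variances:

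| Setting | Bonferroni | Closed test |
|---|---|---|
| Global null, any rejection | 4.2–4.4% | 4.9–5.1% |
| Both exercise arms far from control, true-null exercise pair rejected | 1.7% | 4.9–5.1% |

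In the second setting the first two nulls are almost always rejected, so Holm and Shaffer also test the last pair at 5%.

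**Power, n = 20 per arm, correlation 0.7, pooled-error tests.**

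| True shifts (arm 1, arm 2, control) | Comparison | Bonferroni | Holm | Shaffer | Closed |
|---|---|---|---|---|---|
| 0.6, 0.6, 0 | each exercise arm vs control | 50% | 53% | 57% | 60% |
| 0.8, 0.4, 0 | each smaller difference (arm 2 vs control; arm vs arm) | 21% | 27% | 35% | 36% |

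Over Bonferroni, the gains are 3, 7 and 10 points in the first row and 6, 14 and 15 points in the second.

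**Sensitivity, Bonferroni to closed test.**
- n = 15: 36% to 46% (first row) and 15% to 27% (second row).
- n = 30: 71% to 80% and 33% to 50%.
- Correlation 0.4, n = 20: 24% to 31% (first row).

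**Unequal variances.** With both exercise arms far from control and pooled error, the true-null exercise pair is rejected as follows (SDs of change and arm sizes assumed, in the order Zumba, Stepping, control):

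| SDs of change | n per arm | Bonferroni | Closed test |
|---|---|---|---|
| 1.5, 1, 1 | 20, 20, 20 | 2.6% | 6.8% |
| 1, 1, 0.5 | 20, 20, 20 | 3.9% | 8.9% |
| 1, 1, 0.5 | 14, 14, 20 | 4.6% | 10.3% |

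Holm and Shaffer share that last step at 0.05, so pooled error affects them equally. Testing each pair with its own variances (Welch) brings the rate back to about 5%. Power is then slightly lower for every method and the ordering is unchanged.

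**The case against.** **Bonferroni is a legitimate choice.** This stands: it controls the familywise error, and the point is an inefficiency. It is still a method that section 2.8 fixes, not a detail left open for a statistical analysis plan.

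**The plan might be read as correcting twice, first by the omnibus test and then by Bonferroni.** The text does not support this. It never says that the pairwise comparisons wait for a significant interaction. The case against Bonferroni does not need that reading, because Holm and Shaffer improve on ungated Bonferroni too.

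**A reader might infer that the closed test is better in every trial.** It is not. Ungated Bonferroni rejected a pair that the gated test missed in about 0.5% of simulated trials or fewer. Only Holm and Shaffer never reject less than Bonferroni on the same p-values.

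**Bonferroni's slack absorbs unequal variances.** This stands for pooled-error tests, as the last table shows, and is why the change should come with pair-specific variances.

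**The plan has no stated correction across scores.** True, and loosening the pairwise step adds to that. With four independent scores (assumed), the chance of at least one false arm-against-arm claim is 1 − (1 − 0.017)⁴ = 7% under Bonferroni and 1 − (1 − 0.049)⁴ = 18% when the last pair is tested at about 5%. Neither method was meant to cover this; it needs its own rule.

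**Results are already in the document.** Relaxing the threshold now for data already analysed would be a change made with knowledge of the results. This stands and limits where the fix applies.

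**Conclusion.** The point holds as an optional improvement. If all three pairs are tested, Bonferroni judges each at 0.0167, and a stepwise procedure gives the same 5% familywise guarantee with more power. Under the assumed n = 20 per arm and correlation 0.7, the gain runs from 3 points (Holm) to 10 points (closed test) per exercise-control pair, and from 6 to 15 points for the smaller differences. The size depends on the assumed sample size, effects and correlation, none of which the Protocol gives; the direction does not.

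Nothing here suggests that a reported finding is wrong. A comparison that was significant under Bonferroni would also be significant under Holm or Shaffer on the same p-values.

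**What to change.** In section 2.8, replace the Bonferroni wording with a sentence such as: *For each score, the three pairwise contrasts of change from baseline are tested with Welch's test, using the variances of the two groups compared, and the three p-values are adjusted by Holm's method at a familywise level of 0.05.*

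For exactly three arms, a sharper option may be named instead: Shaffer's form, or the interaction at 0.05 followed by each pair at 0.05. The gated option needs the interaction, not the group main effect, as its gate, and that F test still assumes a common variance. Neither option carries over to four or more arms in this form.

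For data already analysed, keep the Bonferroni decisions as the planned analysis and label any stepwise result post hoc. The new wording applies to analyses not yet run or to a later trial.

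The cost is one sentence, with no new data. The sentence would also settle which pairs and which effect are corrected. The drawbacks are that no simple simultaneous confidence intervals match the stepwise decisions, so ordinary 95% intervals would be reported alongside, and that control is within one score only.

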2.2 Participants

Children diagnosed with Attention Deficit Hyperactivity Disorder were recruited for the study. Participants were within the age range of **8-12** years and were diagnosed according to DSM criteria by a qualified clinician.

Inclusion criteria included:

- A clinical diagnosis of ADHD
- Being within the specified age range
- Ability to follow verbal instructions
- Ability to read and understand Turkish language
- Being under medication at least 2 months prior to the study

Exclusion criteria included:

- Presence of neurological, orthopedic, or psychiatric disorders other than ADHD
- Participation in regular structured exercise programs during the study period
- Inability to perform any physical activity

Written informed consent was obtained from parents or legal guardians prior to participation.

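### The primary cognitive result is stated as improvement in each exercise arm with no reference to control, and section 2.8 does not say which of its two analyses supports a claim of improvement

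*Protocol*

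**What the plan says.** The aim in section 1 is to study the effects of two exercise programmes. The design has three randomised parallel groups, one of them a control group that continues its usual activities (sections 2.1, 2.3 and 2.4). Cognition, measured by tests such as the Stroop and the Visual-Auditory Digit Span, is the primary outcome (section 2.5).

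On timing and tools:
- Section 2.5: "Assessments were conducted at baseline and after the 8-week intervention period".
- Section 2.6: "Post-intervention assessments were performed using the same measurement tools as at baseline".

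On analysis, section 2.8 assigns a two-factor (group × time) repeated measures ANOVA with Bonferroni post hoc correction to the primary outcome variables. It then adds: "Within-group changes were analyzed using paired-samples t-tests". It does not rank the two or say which one a statement of improvement rests on.

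The Results section describes the basis of the cognitive result as "Changes from baseline to post-intervention scores were used to evaluate attention, executive functions, working memory, and cognitive processing speed". The result itself is "Both intervention groups demonstrated improvements in cognitive functions". The next sentence sets the exercise arms against each other: "The Gince Zumba group demonstrated greater gains in attention-related abilities, while the Square Stepping Exercise group showed more pronounced improvements in high-level cognitive functions". For the secondary motor outcome the wording is different: "both intervention groups exhibited significant improvements in motor performance relative to the control group". The behavioural result likewise names control, alongside baseline.

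**The concern.** The Stroop and Digit Span are performance tests. A child who sits them a second time, eight weeks later, may do better because the task is familiar or because the child has developed. A concurrent randomised control arm lets that gain be subtracted. A statement that each exercise arm improved from its own baseline does not subtract it, and so does not answer a question about the effect of exercise.

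The omission affects only the primary outcome. The same short Results section uses control as the comparator for motor performance and for behaviour, so the reader cannot tell whether either programme did better than control on cognition. The conclusion at stake is the trial's headline one.

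**Working it through.** **Step 1: the wording of the three results.**

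| Outcome | Baseline change cited | Control named | Called significant |
|---|---|---|---|
| Cognition (primary) | yes | no | no |
| Motor (secondary) | yes | yes | yes |
| Behaviour (secondary) | yes | yes | yes |

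**Step 2: what each analysis in section 2.8 can show.** Let g be a practice or maturation gain common to all arms, and e the effect of exercise.
- The paired t-test in an exercise arm tests g + e = 0. With e = 0 and g > 0 it still tends towards significance.
- With two time points, the group × time interaction compares mean change across arms. The contrast of an exercise arm with control is (g + e) − g = e, so the shared gain cancels.

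The quoted sentence fits either analysis, and would be satisfied by g alone.

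**Step 3: illustration of size.** The protocol gives no sample size, SD, retest gain or numerical result, so there is no figure of its own to reproduce. Everything below is assumed:
- no exercise effect (e = 0);
- gain d of 0.2, 0.3 or 0.4 SD in every arm;
- test-retest correlation r = 0.7;
- 15, 20 or 30 children per arm;
- one test score, and arms independent;
- two-sided 0.05 level (the protocol states 0.05 but not the sidedness).

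Standardised mean change: dz = d / √(2(1 − r)) = d / √0.6, which gives 0.258, 0.387 and 0.516.

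The paired t statistic is noncentral t with n − 1 degrees of freedom and noncentrality dz√n. The chance of a significant improvement in one arm is p = P(t > critical value). The quoted claim concerns both exercise arms, so the relevant chance is p².

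Example for n = 20, d = 0.4: noncentrality 0.516 × √20 = 2.31, critical value 2.093, p = 0.592, p² = 0.350.

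| n per arm | d = 0.2: one arm / both | d = 0.3: one arm / both | d = 0.4: one arm / both |
|---|---|---|---|
| 15 | 0.15 / 0.02 | 0.29 / 0.08 | 0.46 / 0.21 |
| 20 | 0.19 / 0.04 | 0.38 / 0.14 | 0.59 / 0.35 |
| 30 | 0.28 / 0.08 | 0.54 / 0.29 | 0.78 / 0.61 |

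With no gain at all, p = 0.025 and p² = 0.0006.

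**Step 4: the controlled test on the same assumptions.** With two time points the group × time test is a one-way ANOVA on change scores. In 20,000 simulated trials per setting (n = 15, 20, 30; dz = 0.258 and 0.516 in all three arms), it was significant in 4.8% to 5.1%. The shared gain does not inflate it.

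**The case against.** The strongest reply is that the plan already deals with the threat. Section 2.8 assigns the group × time model to the primary outcomes, and that model removes any shared gain. The paired t-tests are tied only to within-group change and are given no stated role in an efficacy conclusion. The sentence contrasting the two exercise arms makes a between-arm comparison, which a paired t-test cannot supply, so the ANOVA and its post hoc tests may well lie behind the paragraph. The cognitive sentence does not use the word significant, so linking it to a paired test at 0.05 is inference. All the numerical inputs above are assumed.

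Most of this stands. A reader might infer that the primary conclusion rests on the paired t-tests, or that the reported cognitive benefit is spurious. The document supports neither: it does not say which test lies behind the sentence, gives no numbers, and does not show that a retest gain occurred. A reader might also take the one-arm probabilities as the size of the problem, but the claim is about both arms, for which the chances are lower.

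The reply does not remove the gap. A controlled model is specified, yet the stated result does not report what it found against control. A contrast between two exercise arms does not show that either one beat control.

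**Conclusion.** The point holds as a fault in how the primary result is stated and in section 2.8's silence on which analysis supports a claim of improvement. It is not the absence of a controlled analysis. That the cognitive paragraph omits control, while both secondary results name it, can be read directly from the text.

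The size is illustrative only. Under the assumptions listed, a shared gain alone makes both exercise arms significantly improved on one score with probability from 0.02 (15 per arm, 0.2 SD) to 0.61 (30 per arm, 0.4 SD), against about 0.05 for the group × time test. A different gain, correlation, sample size or number of scores would change these figures. They show what the wording permits, not what happened in this trial.

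**What to change.** - In section 2.8, state that efficacy on the Stroop and Digit Span is concluded from the group × time interaction and from the Bonferroni-adjusted contrast of each exercise arm's change minus the control arm's change, with a 95% CI.
- Label the paired t-tests descriptive.
- In the Results, show the control arm's change and reword the primary cognitive result as the comparison with control. If that comparison is not significant, say that improvement over control was not shown.

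No new data or model are needed: the control arm was assessed and the ANOVA is already specified. The work is re-reporting and rewording. The cost is that the cognitive claim may become less favourable.
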